**Figure 1. Study B1931022: Kaplan Meier Curve for Overall Survival (Intent to Treat Population)**

### 2.2.2.1.2. Pharmacokinetic

Based on PK data from 163 patients in Study B1931022, mean peak and trough exposures of inotuzumab ozogamicin increased with each cycle, due to its long steady state elimination half life (12.3 days). Mean peak concentrations in serum were observed at or near the end of infusion with a highest observed mean peak concentration of 308 ng/mL by Cycle 4 Day 1 and the highest observed mean trough concentration of 91.3 ng/mL, by Cycle 4 Day 8, compared to a peak of 211 ng/mL at Cycle 1 Day 1 and a trough of 6.84 ng/mL at Cycle 1 Day 8.

Based on the exposure response analyses of the safety and efficacy data from Phase 3 Study B1931022 and Phase 1/2 Study B1931010, there was a statistically significant ( $p<0.0001$ ) relationship between inotuzumab ozogamicin average serum concentration up to the time of response ( $C_{avg}$ ) and the probability of CR/CRi and MRD negativity. Furthermore, there was a statistically significant ( $p<0.05$ ) relationship between inotuzumab ozogamicin cumulative total serum exposure during Cycle 1 ( $cAUC_{P1}$ ) and the probability of VOD (VOD per assessment of the independent Hepatic Events Adjudication Board (HEAB) for Phase 3 Study B1931022).

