### 3. OBJECTIVES, ESTIMANDS, AND ENDPOINTS

Objectives	Estimands	Endpoints
Primary:		

To evaluate the efficacy of inotuzumab ozogamicin based on a primary endpoint of complete remission [CR]/complete remission with incomplete hematologic recovery [CRi] per Investigator's assessment in Chinese adult patients with relapsed/refractory B-cell ALL.

	

The treatment effect of inotuzumab ozogamicin from the time of first dose until end of treatment for all patients who received at least one dose of inotuzumab ozogamicin regardless of tolerability and duration on treatment.

	

CR/CRi per investigator's assessment.

Objectives	Estimands	Endpoints
Secondary:		

To evaluate the efficacy of inotuzumab ozogamicin.

To evaluate the safety of inotuzumab ozogamicin.

To evaluate PK of inotuzumab ozogamicin

To evaluate the immunogenicity of inotuzumab ozogamicin

		

Duration of remission (DoR).

Minimal residual disease (MRD) negativity in patients achieving CR/CRi.

Progression-free survival (PFS).

Overall survival (OS).

Hematopoietic stem cell transplant (HSCT).

AEs and laboratory abnormalities by type, frequency, severity (as graded by NCI CTCAE v5.0), timing, seriousness, and relationship to study therapy, including VOD (total, during study treatment, and post-HSCT).

Inotuzumab ozogamicin <math>C_{max}</math> and <math>C_{trough}</math>.

Incidence of anti-drug antibodies (ADA) and neutralizing antibodies (NAb).

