#### **Reporting of AESI With Immediate Notification**

Investigator should notify the sponsor immediately (ie, within 24 hours) of the following events, as per SAE notification and/or using the pregnancy form (whichever is applicable):

- Hy's Law cases (see [Section 10.5](#))
- Potential VOD/SOS Cases (see [Section 8.4.8.2](#))
  - All suspected cases of hepatic SOS, irrespective of timing, causality and severity, should be reported in the AE CRF. If the event is deemed serious by the investigator, the SAE reports should include a complete list of all anticancer therapy administered before, during and after study therapy, including pre- and post-study HSCT conditioning, GVHD prophylaxis and treatment, and all concomitant medications used for prevention of hepatic toxicity (eg, ursodiol, defibrotide, low molecular weight heparin) and/or for the treatment of SOS (ie, defibrotide).

- Exposure during Pregnancy (see [Section 8.4.5.1](#))
- Second primary malignancy

Reporting of AESI Without Immediate Notification (unless assessed as SAE [see [Section 8.4.1.1](#) for reporting timeframe])

- Neurotoxicity
- Nephrotoxicity
- QT abnormalities (defined as Grade 3, 4, prolongation or QTcF post-baseline absolute value of >500 msec)
- Interstitial lung disease
- Pancreatitis
- Myelosuppression/cytopenia including Infections and Hemorrhages

AESIs are examined as part of routine safety data review procedures throughout the clinical trial and as part of signal detection processes. Should an aggregate analysis indicate that these prespecified events occur more frequently than expected, eg, based on epidemiological data, literature, or other data, then this will be submitted and reported in accordance with Pfizer's safety reporting requirements. Aggregate analyses of safety data will be performed on a regular basis per internal SOPs.

All AESIs must be reported as an AE or SAE following the procedures described in [Sections 8.4.1](#) through [8.4.4](#). An AESI is to be recorded as an AE or SAE on the CRF. In addition, an AESI that is also an SAE must be reported using the CT SAE Report Form.

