#### 9.4.2. Safety Analyses

The safety analysis will be conducted on the safety population. AEs will be presented with and without regard to causality based on the Investigator's judgment. The frequency of overall toxicity, categorized by toxicity Grades 1 through 5, will be described. Additional summaries will be provided for AEs that are observed with higher frequency.

Rate of VOD/SOS (total, on-study treatment, and post-HSCT) will be summarized in the safety population. Descriptive analyses (ie, the number, percent of patients with VOD along with 2-sided 95% CI) will be presented. A subgroup analysis will also be conducted for VOD in patients who undergo HSCT in the safety population. Analyses in this subgroup will include an assessment of VOD in all patients with a subsequent HSCT as well as in patients who proceed to HSCT directly after inotuzumab ozogamicin treatment (without an intervening induction therapy). All known cases of VOD, regardless of causality and severity, will be reported as SAEs for the entire duration of study participation, including the Follow-up period.

Drug exposure will be summarized using descriptive statistics.

Laboratory data will be summarized by the type of laboratory test. Summary of Laboratory abnormalities will be presented by maximum CTCAE Grade. A shift summary of baseline grade by maximum post-baseline grade will also be presented. Parameters which cannot be graded will be summarized relative to the normal range (ie, higher or lower than normal range). Vital signs data will be summarized using descriptive statistics (mean, standard deviation, median, quartiles, minimum, and maximum) of actual values and change from baseline for each nominal visit over time (ie, unscheduled assessments will be excluded).

The number and percentage of patients with abnormal findings in physical examination will be summarized by body system for each nominal assessment timepoint.

Exploratory analysis may be performed to assess relationship between CD22 and efficacy (including MRD) and/or safety outcomes if data permit, the details will be decrypted in the SAP.

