2.2. Study Design

This is an open-label, multi-center, single arm, phase 4 study of inotuzumab ozogamicin in Chinese adult participants with relapsed or refractory CD22-positive acute lymphoblastic leukemia (ALL), serving as a post approval commitment (PAC) study to confirm the efficacy, safety and pharmacokinetics (PK) of inotuzumab ozogamicin.

This study is designed to be a hypothesis test. A total of 44 participants will be enrolled to receive inotuzumab ozogamicin, which will provide at least 90% power to reject the null hypothesis ($H_0: CR/CRi \text{ rate} \leq 37\%$) when the true CR/CRi rate $\geq 61\%$ under the 1-sided significance level 0.025. Assuming exactly 44 participants are enrolled, the null hypothesis will be rejected and it will be concluded that the study has demonstrated that the true CR/CRi rate exceeds 37% if 23 or more responders are observed. However, at the time of the analysis, the testing will depend on the actual number of participants enrolled.

Two cycles of treatment of inotuzumab ozogamicin are recommended for hematopoietic stem cell transplant (HSCT) if the participant achieves response within the time period and a suitable donor is available, otherwise one more cycle, ie, the third cycle, may be considered. For participants not proceeding to HSCT, the maximum length of treatment is 6 cycles.

All cases of veno occlusive disease (VOD, also known as sinusoidal obstruction syndrome, SOS) irrespective of causality or severity will be reported as serious adverse events (SAEs) for up to 2 years after the first dose of inotuzumab ozogamicin. An independent hepatic event adjudication committee will evaluate safety for potential VOD/SOS events. Survival will be followed up to 2 years from the first dose of inotuzumab ozogamicin.

The end of the study is defined as the date of completion of survival follow-up for the last participant, which corresponds to up to 2 years from the date of last participant first dose.

This study will also use a hepatic events adjudication board (HEAB). The HEAB will review safety data, eg, potential cases of VOD.

No formal interim analysis will be conducted for this study.

This study will not use a data monitoring committee (DMC).

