6.6.1.1. Adverse Events of Special Interest

All cases of VOD/SOS irrespective of causality or severity will be reported as SAEs for up to 2 years after the first dose of inotuzumab ozogamicin.

If data permits, number and percentage in patients with VOD/SOS and in patients with VOD/SOS following post-study HSCT will be summarized. The VOD/SOS patients above are also summarized considering different risk factors, including prior study HSCT (yes/no), prior history of hepatic disease (yes/no), baseline ALT/AST/Total serum bilirubin abnormal by CTCAE (Grade 0,1).

Summary of AESI by PT will also be provided.

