8.2. Appendix 2. Definitions of Adverse Events of Special Interest

IMPORTANT IDENTIFIED RISKS

- Grade ≥ 3 hepatotoxicity and/or serious hepatotoxicity, including VOD/SOS.

GRADE ≥ 3 HEPATOTOXICITY AND/OR SERIOUS HEPATOTOXICITY, INCLUDING VOD/SOS AEs will be defined as:

- Grade ≥ 3 AEs and/or SAEs retrieved by applying the following MedDRA SMQs: Cholestasis and jaundice of hepatic origin (SMQs narrow); Hepatic failure, fibrosis, cirrhosis, and other liver damage related conditions (SMQs narrow); Hepatitis, noninfections (SMQs narrow); Liver related investigations signs and symptoms (SMQs narrow and broad);
- Grade ≥ 3 AEs and/or SAEs encoded to the following MedDRA PTs: Hepatic vein occlusion, Hepatic vein thrombosis, Portal vein thrombosis, Budd-Chiari Syndrome, Chronic graft-versus-host disease in liver, and Acute graft-versus-host disease in liver;
- All AEs encoded to the following MedDRA PTs: Venoocclusive liver disease and Venoocclusive disease.
- Myelosuppression/cytopenia.

MYELOSUPPRESSION/CYTOPENIA AEs will be defined as:

- Any reported PTs retrieved by applying the following MedDRA SMQs: Haematopoietic thrombocytopenia (SMQ narrow and broad), Haematopoietic leukopenia (SMQ narrow), Haematopoietic erythropenia (SMQ narrow and broad), and Haematopoietic cytopenias affecting more than one type of blood cell (SMQ narrow).

INFECTION AEs (not considered a separate risk, but considered to be complications of myelosuppression/cytopenia) will be defined as:

- Any reported PTs retrieved by applying the MedDRA SOC: Infections and Infestations.

HAEMORRHAGE AEs (not considered a separate risk, but considered to be complications of myelosuppression/cytopenia) will be defined as:

- Any reported PTs retrieved by applying the MedDRA SMQ: Haemorrhage terms (excluding laboratory terms) (SMQ narrow).

IMPORTANT POTENTIAL RISKS

- Interstitial lung disease (ILD).

INTERSTITIAL LUNG DISEASE AEs will be defined as:

- Any reported PTs retrieved by applying the MedDRA SMQ: Interstitial lung disease (SMQ narrow);
- All AEs encoded to the following MedDRA PT: Graft versus host disease in lung.
- Inflammatory gastrointestinal events.

INFLAMMATORY GASTROINTESTINAL EVENT AEs will be defined as:

- Any reported PTs retrieved by applying the MedDRA Version SMQ Gastrointestinal nonspecific inflammation (SMQ narrow);
- All AEs retrieved by applying the MedDRA higher level term (HLT) Colitis (excluding infective) (all paths) and Stomatitis and ulceration (all paths);

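### The VOD/SOS rate rests on investigator AE terms that take in suspected cases, and no planned analysis uses the independent committee's adjudicated result

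*SAP*

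**What the plan says.** VOD is a named part of the secondary safety endpoint. Protocol section 3 lists AEs and laboratory abnormalities, "including VOD (total, during study treatment, and post-HSCT"). Protocol section 9.4.2 repeats the three-way split: "Rate of VOD/SOS (total, on-study treatment, and post-HSCT) will be summarized in the safety population". It adds a two-sided 95% CI.

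The SAP handles it in two places.

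- Section 3.5.1 sends the reader to Appendix 2 for the AESI definitions. There, inside the composite of grade 3 or higher and/or serious hepatotoxicity, the VOD/SOS component is "All AEs encoded to the following MedDRA PTs: Venoocclusive liver disease and Venoocclusive disease".
- Section 6.6.1.1 plans the count: "If data permits, number and percentage in patients with VOD/SOS and in patients with VOD/SOS following post-study HSCT will be summarized". It does not say what makes a patient a case. It also does not repeat the during-treatment split or the CI.

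The AE page that feeds those terms is deliberately broad. The protocol's AESI section says "All suspected cases of hepatic SOS, irrespective of timing, causality and severity, should be reported in the AE CRF".

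Both documents also set up adjudication. SAP section 2.2 states "An independent hepatic event adjudication committee will evaluate safety for potential VOD/SOS events", and protocol sections 8.3.5 and 9.5.2 give the committee the same task, with Hy's law cases added. Further detail is left to a charter held by the sponsor.

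**The concern.** The trial collects VOD/SOS through a wide net, as safety surveillance should, and then has an independent committee sort the potential cases. The SAP carries only the first step into the analysis. Read as written, an event that stays coded to one of the two preferred terms counts as VOD even if the committee rejects it. An event that the committee judges to be VOD but that is coded elsewhere does not count.

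At stake is the estimate of the drug's best-known serious hepatic risk, in a study meant to confirm safety in Chinese patients. Few events are expected, so the classification of one or two patients is visible in the rate. If the plan does not say which classification defines a case, the choice could also be made after results are known, in an open-label study.

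**Working it through.** **1. Trace of the case definition**

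| Step | Where | Case status used |
|---|---|---|
| Collection | Protocol 8.4.8, AESI with immediate notification | All suspected cases go on the AE page |
| Diagnostic criteria | Protocol 8.4.8.2 | Given, but timed from transplant and linked to no analysis definition |
| Levels of certainty | Protocol 7.1.1.1 | Possible, probable and confirmed are distinguished; the SAP does not carry this over |
| Adjudication | Protocol 8.3.5 and 9.5.2; SAP 2.2 | Committee reviews potential cases; no output variable is named |
| Analysis definition | SAP 3.5.1 and Appendix 2 | AEs coded to two preferred terms |
| Rate | SAP 6.6.1.1; Protocol 9.4.2 | Source of case status not stated |

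Neither document names an adjudicated category, a rule for disagreement between investigator and committee, or a table, listing or sensitivity analysis that uses the committee's result. That SAP 6.6.1.1 draws on the Appendix 2 terms is a reading, but the SAP offers no other definition.

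**2. Denominator**

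The plan states no expected VOD rate or precision, so there is no VOD figure to reproduce. The denominator does reproduce. With the Wald formula in SAP 5.1.1, n = (1.96 + 1.282)² × 0.61 × 0.39 / (0.61 − 0.37)² = 43.4, rounded up to 44.

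**3. Expected counts**

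The inputs are the Phase 3 figures in protocol sections 2.2.2.1.1 and 2.2.2.1.3.1: VOD in 23/164, follow-up HSCT in 79/164, and VOD after HSCT in 18/79.

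- All participants: 44 × 23/164 = 6.2, taken as 6.
- Transplanted: 44 × 79/164 = 21.2, taken as 21.
- VOD after HSCT: 21 × 18/79 = 4.8, taken as 5.

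**4. Effect of reclassification**

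The interval is Clopper-Pearson, two-sided 95%. The number of reclassified cases is an assumption, because the documents give no confirmation rate.

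| Change from the expected count | All participants | Transplanted |
|---|---|---|
| One more judged VOD | 7/44 = 15.9% (6.6 to 30.1) | 6/21 = 28.6% (11.3 to 52.2) |
| None | 6/44 = 13.6% (5.2 to 27.4) | 5/21 = 23.8% (8.2 to 47.2) |
| 1 not confirmed | 5/44 = 11.4% (3.8 to 24.6) | 4/21 = 19.0% (5.4 to 41.9) |
| 2 not confirmed | 4/44 = 9.1% (2.5 to 21.7) | 3/21 = 14.3% (3.0 to 36.3) |
| 3 not confirmed | 3/44 = 6.8% (1.4 to 18.7) | 2/21 = 9.5% (1.2 to 30.4) |

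Each reclassified case moves the overall rate by 1/44 = 2.3 points and the post-HSCT rate by 1/21 = 4.8 points. The two columns are separate illustrations.

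**The case against.** The strongest reply is that the AE record is more than raw suspicion. Protocol 8.4.8.2 sets diagnostic criteria and asks for a hepatology work-up in serious or severe hepatic events, with Doppler ultrasound when VOD is in the differential. Appendix 3 asks investigators to establish a diagnosis where possible and to record updated information. Counting every reported case is also a defensible, cautious safety rule. The VOD analysis is descriptive, with no threshold attached, and the intervals above overlap heavily. All of this stands. It limits how much mixing to expect, but it does not put the committee's result into any analysis.

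The charter may say more. The claim here covers only what the protocol and SAP describe. Which classification defines an analysed endpoint still belongs in the SAP.

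A reader might infer three stronger points that the documents do not support.

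- **The reported rate is biased upwards.** Rejected cases would lower it. But the same committee also sees Hy's law cases, and it could recognise VOD in events coded to other terms. No reclassification rate is given in either direction.
- **The rate is not comparable with the Phase 3 rate.** Protocol 2.2.2.1.2 ties adjudication ("VOD per assessment of the independent Hepatic Events Adjudication Board (HEAB) for Phase 3 Study B1931022") to the exposure-response analysis only. The 14% in section 2.2.2.1.3.1 is not described as adjudicated, so investigator-reported VOD may be the like-for-like basis.
- **The adjudicated rate must be the main one.** That is a preference. Showing both is enough.

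**Conclusion.** The point holds as a gap in the analysis plan that is cheap to close. The SAP defines VOD/SOS by two coded terms from a page that takes suspected cases, and no described analysis uses the adjudicated outcome. The reported rate can therefore mix confirmed and unconfirmed cases and can miss adjudicated VOD coded elsewhere.

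The net error is of unknown direction and size. What can be said is how sensitive the rate is: 2.3 points per case overall, and 4.8 points per case after HSCT if about 21 participants are transplanted. If 1 to 3 of 6 expected cases were not confirmed, 13.6% would become 11.4% to 6.8%.

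These figures rest on the Phase 3 rates carrying over and on an assumed number of reclassified cases. The primary endpoint, the sample size and the decision rule are unaffected.

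**What to change.** Before database lock, amend SAP 6.6.1.1 as follows.

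1. State that the planned VOD/SOS rate is investigator-reported and uses the Appendix 2 terms.
2. Add beside it the committee-confirmed rate in the safety analysis set: total, during treatment and post-HSCT, each with an exact 95% CI. This also brings the section into line with the split and interval promised in protocol 9.4.2.
3. Add a listing of agreement between investigator and committee for each reviewed event, including events judged to be VOD but coded to other terms.

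The cost is one table, one listing and the transfer of the committee's outcomes to the analysis database; neither document says that those outcomes are already held there. No clinical procedure changes, and the reported rate stays visible, so no signal is hidden. As an editorial matter, use one name for the committee: the protocol calls it HEAC, while SAP 2.2 describes it once as a committee and once as HEAB.

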3.5. Safety Endpoints

Safety endpoints will be summarized based on the on-treatment period unless otherwise specified.

On-treatment is defined as the time from the first dose of study treatment through minimum (9 weeks after the last administration of the investigational product, start day of new anti-cancer therapy – 1 day). The start date of new anti-cancer therapy after the first dose of study treatment is derived as outlined in [Section 5.2.5](#). Adverse events occurring on the same day as the first dose of study treatment will be considered to have occurred during the on-treatment period. All other assessments which occur on the same day as the first dose of study treatment will be considered baseline assessments (see [Section 3.4](#) for the definition of baseline). If the exact time is collected, the last assessment before the time of first dose of study treatment will be considered as baseline assessments.

Safety data collected outside the on-treatment period as described above will be listed but not summarized.

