3.5.1. Adverse Events

Adverse events (AEs) will be coded to preferred term (PT) and system organ class (SOC) using the Medical Dictionary for Regulatory Activities (MedDRA) and classified by severity using the National Cancer Institutes (NCI) Common Terminology Criteria for Adverse Events (CTCAE), version 5.0. For other AEs without specific NCI CTCAE v5.0 definitions, results will be identified according to NCI CTCAE v5.0 “other” categories.

An event will be considered treatment related if the investigator considers so.

An adverse event is considered treatment-emergent relative to a given treatment if the event start date is during the on-treatment period (including on the date of first dose). All cases of VOD/SOS irrespective of causality or severity will be reported as SAEs for up to 2 years after the first dose of inotuzumab ozogamicin.

Adverse Events of Special Interest (AESI)

AEs of special interest (AESI) are as follows:

- GRADE ≥ 3 HEPATOTOXICITY AND/OR SERIOUS HEPATOTOXICITY, INCLUDING VOD/SOS;
- MYELOSUPPRESSION/CYTOPENIA;
- INTERSTITIAL LUNG DISEASE;
- INFLAMMATORY GASTROINTESTINAL EVENT;
- PANCREATITIS;
- SECONDARY PRIMARY MALIGNANCY;

- REPRODUCTIVE AND DEVELOPMENT TOXICITY;
- NEPHROTOXICITY; and
- NEUROTOXICITY.

These events are defined in [Appendix 2](#).

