5.2. General Methods

Except the hypothesis testing for CR/CRI, all analyses will be descriptive.

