6.6.1. Adverse Events

All analyses will be based on treatment emergent events unless otherwise specified. Treatment emergent is defined in [Section 3.5.1](#). AEs not considered treatment emergent will be flagged in data listings.

A high level summary of TEAEs (all causality), TEAEs (treatment related) and Cycle 1 TEAEs (treatment related) will include the number and percentage of participants with:

- Any TEAE;
- Serious TEAE;
- TEAE with CTCAE Grade 3-4;
- Grade 5 TEAE;

- TEAEs leading to dose reductions of inotuzumab ozogamicin;
- TEAEs leading to dose delay of inotuzumab ozogamicin;
- TEAEs leading to permanent discontinuation of inotuzumab ozogamicin.

Additionally, the number of events reported for each of the categories above will be provided. Each unique adverse event at the PT level for a participant is included in the count.

Seriousness, toxicity grade, action taken (interruption, reduction, and withdraw) are as reported by the investigator on the adverse event CRF.

Summaries of TEAE by SOC and PT in decreasing frequency will be provided for:

- TEAEs (All Causality);
- TEAEs by Maximum Toxicity Grade (All Causality);
- TEAEs (Treatment related);
- TEAEs by maximum toxicity grade (Treatment related);
- Serious TEAEs (All causality);
- Post-HSCT SAE (All causality);
- Serious TEAEs (Treatment related); and
- Post-HSCT SAE (Treatment related).

An event will be considered treatment related if the investigator considers so.

The following summaries will be provided by PT only (ie, summaries will not include SOC) in decreasing frequency:

- TEAEs (All causality);
- TEAEs (All causality) experienced by $\geq 10\%$ of participants;
- TEAEs (All causality) by maximum toxicity grade;
- Grade 3-5 TEAEs (All causality and Treatment related);
- TEAEs leading to dose delays of inotuzumab ozogamicin (all causality);
- TEAEs leading to dose reductions of inotuzumab ozogamicin (all causality);

- TEAEs leading to permanent discontinuation of inotuzumab ozogamicin (all causality);
- Serious TEAEs (all causality); and
- Post-HSCT SAEs (all causality).

Each participant will be counted only once within each SOC and PT.

As described in [Section 5.3](#), in case a participant has events with missing and/or non missing toxicity grades, the maximum of the non-missing grade will be displayed. Missing grade will only be displayed in the event that only one event has been reported for a participant and the grade is missing.

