- All AEs encoded to the following MedDRA PTs: Oral pain, Oropharyngeal pain, and Mucosal inflammation.
- Pancreatitis

PANCREATITIS AEs will be defined as:

- Any reported PTs retrieved by applying the MedDRA Version SMQ: Acute pancreatitis (SMQ narrow);
- All AEs encoded to the following MedDRA PTs: Amylase abnormal, Amylase creatinine clearance ratio abnormal, Amylase increased, Lipase abnormal, Lipase increased, Lipase urine increased, Pancreatic enzyme abnormality, Pancreatic enzymes abnormal, and Pancreatic enzymes increased.
- Second primary malignancy.

SECONDARY PRIMARY MALIGNANCY AEs will be defined as:

- Any reported PTs retrieved by applying the MedDRA SOC: Neoplasms benign, malignant and unspecified (including cysts and polyps).

- Reproductive and developmental toxicity (post exposure during pregnancy and while breast feeding).

REPRODUCTIVE AND DEVELOPMENT TOXICITY AEs will be defined as:

- Any reported PTs retrieved by applying the following MedDRA SMQs: Termination of pregnancy and risk of abortion (SMQ narrow), Fertility disorders (SMQ narrow and broad), Foetal disorders (SMQ narrow and broad), Neonatal disorders (SMQ narrow and broad), Congenital, familial, and genetic disorders (SMQ narrow);
- All AEs encoded to the following MedDRA PTs: Pregnancy of partner, Exposure via father, Foetal exposure during pregnancy, and Maternal exposure during pregnancy.
- Nephrotoxicity.

NEPHROTOXICITY AEs will be defined as:

- Any reported PTs retrieved by applying the following MedDRA SMQ: Acute renal failure (SMQ narrow and broad).
- Neurotoxicity.

NEUROTOXICITY AEs will be defined as:

- Any reported PTs retrieved by applying the following MedDRA SMQs: Demyelination (SMQ narrow and broad) and Peripheral neuropathy (SMQ narrow and broad) and by searching for the following specific PTs under the higher level term: Cranial nerve disorders NEC (all paths).

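### The SAP defines the second primary malignancy AESI by the whole Neoplasms SOC, so benign neoplasm, cyst or polyp terms can be reported under a malignancy label

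*SAP*

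**What the plan says.** Protocol 8.4.8, under immediate notification, says "Investigator should notify the sponsor immediately (ie, within 24 hours) of the following events", and second primary malignancy is on that list. SAP 3.5.1 carries the event over as "SECONDARY PRIMARY MALIGNANCY" and refers to Appendix 2 for its definition, so Appendix 2 is the operative text. There the event stands among the important potential risks, and its only definition is "Any reported PTs retrieved by applying the MedDRA SOC: Neoplasms benign, malignant and unspecified (including cysts and polyps" (the closing bracket of the SOC name is cut off here).

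Four other SAP rules decide what happens to the retrieved terms:

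- Section 6.6.1.1: "Summary of AESI by PT will also be provided".
- Section 6.6.1: "All analyses will be based on treatment emergent events unless otherwise specified".
- Section 3.5: the on-treatment period runs from first dose to 9 weeks after the last dose, or to the day before new anti-cancer therapy if that is earlier. "Safety data collected outside the on-treatment period as described above will be listed but not summarized".
- Section 5.2: apart from the CR/CRi hypothesis test, "all analyses will be descriptive".

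**The concern.** The label and the search do not describe the same thing. The label is a malignancy. The search covers a SOC whose title expressly takes in benign and unspecified neoplasms, cysts and polyps. A reader of the AESI summary will take the label at face value.

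Safety is one of the stated purposes of this post-approval commitment study, and the planned size is 44. In a study this small, a single benign finding under a malignancy AESI can look like a signal. The SAP category would also no longer correspond to the protocol event that it is meant to report.

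The definition has no exclusion for the ALL under study either, which raises the question whether leukaemia terms could appear under the same label.

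**Working it through.** The plan gives no figure on this point to reproduce. The check is mainly a comparison of texts, with a short calculation of the period in which an event could count.

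**1. Label against search.** Label: second primary malignancy (protocol 8.4.8; SAP 3.5.1 and Appendix 2, which also varies between second and secondary). Search: every PT in the Neoplasms SOC. The SOC title alone shows that the search is wider than the label.

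**2. Does anything narrow it?** SAP 3.5.1, 6.6.1, 6.6.1.1 and Appendix 2 contain no restriction to malignant terms, no list of excluded terms and no medical review between retrieval and labelling. Appendix 2 presents the retrieved PTs as the definition of the AESI, not as a first screen.

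**3. Comparison within Appendix 2.** One other item uses a whole SOC: "Any reported PTs retrieved by applying the MedDRA SOC: Infections and Infestations". Its label is infection, so label and search agree. Elsewhere the appendix does narrow: haemorrhage uses a narrow SMQ without laboratory terms. The neoplasm item has neither feature.

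**4. Path rule.** The appendix specifies all paths for the colitis, stomatitis and cranial nerve searches. It gives no path rule for the Neoplasms SOC. The exact set of retrieved PTs is therefore not fixed by the text.

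**5. Terms for the ALL under study.** Three conditions must all hold before such a term appears here:

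- It must be recorded as an AE. Protocol 8.4.7 and the last part of 10.3.2 require recording when the outcome is fatal. The list in 10.3.1 of events that are not AEs, and the opening of 10.3.2, point the other way.
- It must start in the on-treatment period.
- It must be coded to a PT in this SOC. The documents do not state how it would be coded.

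**6. Size.** One patient of 44: 1/44 = 2.3%. The documents give no rate of benign neoplasms, cysts or polyps, and none is assumed.

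**7. Length of the window.** Inputs:

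- SAP 5.2.4: doses on Days 1, 8 and 15; cycle 1 of 21 to 28 days; later cycles of 28 days; at most 6 cycles.
- SAP 3.5: 9 weeks = 63 days after the last dose.

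With no delays and no new anti-cancer therapy:

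| Case | Last dose | End of window |
|---|---|---|
| Single dose | Day 1 | 1 + 63 = Day 64 |
| Six cycles, cycle 1 of 21 days | 1 + 21 + 4×28 + 14 = Day 148 | 148 + 63 = Day 211 (30.1 weeks) |
| Six cycles, cycle 1 of 28 days | 1 + 28 + 4×28 + 14 = Day 155 | 155 + 63 = Day 218 (31.1 weeks) |

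For a more typical case, protocol 2.2.2.1.3 reports a median treatment duration of 8.9 weeks in Study B1931022. Adding 9 weeks gives 17.9 weeks, or about 18.

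**The case against.** The strongest defence is that Appendix 2 is deliberately sensitive throughout. Pancreatitis takes in raised amylase and lipase, interstitial lung disease takes in graft versus host disease in lung, inflammatory gastrointestinal events take in oral pain, and nephrotoxicity and neurotoxicity use broad SMQs. A wide net for neoplasms fits that pattern. Because the output is by PT, a benign term would still read as benign. The SAP plans no category total and shows no table layout. True second primary malignancies reach the sponsor within 24 hours by another route, so detecting them does not depend on this search.

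Much of this stands, and it limits the weight of the point. It does not remove it. The wide terms elsewhere are surrogates for, or relatives of, the event named in the label. A benign neoplasm is neither: it is what the word malignancy excludes.

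Two stronger readings are tempting, and the documents do not support them:

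- A reader might infer that every benign tumour, cyst or polyp would be reported here. Without a path rule and the coding of each term, the text supports only that such terms can be.
- A reader might infer that leukaemia deaths would appear as second primary malignancies. That rests on coding the documents do not state, and on AE recording rules on which the protocol disagrees with itself.

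The window figures are also nominal. Dose delays could move the end past Day 218, and new anti-cancer therapy would bring it forward.

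**Conclusion.** The point holds. As written, the rule can classify non-malignant terms under a malignancy AESI, and no other text corrects it. That conclusion rests on the title of the SOC and on the absence of any narrowing text, and assumes nothing about event rates.

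The consequence is modest: a possible mislabelling in a descriptive summary by PT, where each patient affected is 2.3% of 44 and only events in the on-treatment period count. The expected number of such patients cannot be derived from the documents. It would be going too far to infer an inflated category count, since none is planned, or any effect on the CR/CRi test. Terms for the ALL under study remain an open possibility. The correction is worth making because it is cheap and brings the SAP back into line with the protocol AESI.

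**What to change.** In SAP Appendix 2:

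- Restrict the second primary malignancy definition to malignant terms, which removes benign neoplasm, cyst and polyp terms.
- Exclude terms that denote the ALL under study, such as relapse, recurrence, progression or infiltration.
- State whether the search uses primary path or all paths.
- Show unspecified neoplasm terms separately, and check them against the second primary malignancies notified under protocol 8.4.8, so that a new mass not yet characterised is not lost.
- Fix the resulting PT list before database lock.

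The cost is a short SAP edit and a little term review. No new data are needed, because the event is already notified to the sponsor.

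As a separate item, protocol 8.4.7, 10.3.1 and 10.3.2 should be reconciled on whether death due to progression is recorded as an AE and SAE. That is a change of protocol wording and does not depend on the edit to Appendix 2.
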